#### **GPP ONLY**

- Change from baseline in assessment of dermal symptoms total score
- Change from baseline in systemic symptoms and laboratory findings total score
- Change from baseline in GPP severity index total score.

## **6.12. Health Outcomes/Quality-of-Life Analyses**

[Table RHC.V.6.2](#) includes the description and derivation of the health outcomes measures.

Summaries of health outcomes measures will be provided in patients with GPP and EP separately for Period 2 and for Combined Periods 2 and 3, respectively (Analysis population: FAS Population for Period 2, Maintenance Dosing Period Population for Combined Periods 2 and 3).

By-patient listings of each health outcome measure will be provided (Analysis population: FAS Population).

**Table RHCV.6.2. Description and Derivation of Health Outcomes Measures**

Measure	Description	Variable	Derivation / Comment	Imputation Approach if with Missing Components
Itch NRS	Itch Numeric Rating Scale (NRS): is a single-item, patient-reported outcome (PRO) measure designed to capture information on the overall severity of a patient’s itching due to their psoriatic skin condition by having the patient circle the integer that best describes the worst level of itching in the past 24 hours on an 11-point NRS anchored at 0 representing “no itching” and 10 representing “worst itch imaginable.” (Kimball et al. 2016)	Itch NRS score	Range from 0 to 10.	Single item, missing if missing
		Itch NRS change from baseline	Calculated as: observed Itch NRS – baseline Itch NRS	Missing if baseline or observed value is missing
		Itch NRS ≥4 point reduction from baseline	Reduced/decreased of ≥4 point from baseline	Missing if baseline or observed value is missing
DLQI	Dermatology Life Quality Index (DLQI): is a validated, dermatology-specific, patient-reported measure that evaluates patient’s health-related QoL. This questionnaire has 10 items that are grouped in 6 domains, including symptoms and feelings, daily activities, leisure, work and school, personal relationships, and treatment. The recall period of this scale is over the “last week”. Response categories and corresponding scores are: Very much = 3 A lot = 2 A little = 1 Not at all = 0 Not relevant = 0 (Finlay and Khan 1994; Basra et al. 2008)	DLQI symptoms and feelings domain	Sum of responses of questions #1 and #2: #1. How itchy, sore, painful or stinging has your skin been? #2. How embarrassed or self-conscious have you been because of your skin?	If one question in a domain is missing, that domain is missing.
		DLQI daily activities domain	Sum of responses of questions #3 and #4: #3. How much has your skin interfered with you going shopping or looking after your home or yard? #4. How much has your skin influenced the clothes you wear?	If one question in a domain is missing, that domain is missing.
		DLQI leisure domain	Sum of responses of questions #5 and #6: #5. How much has your skin affected any social or leisure activities? #6. How much has your skin made it difficult for you to do any sport?	If one question in a domain is missing, that domain is missing.
		DLQI work and school domain	Sum of responses of questions question #7A and #7B: #7A. Has your skin prevented you from working or studying? #7B. If No: how much has your skin been a problem at work or studying?	If the answer to question #7A is missing, this domain is missing. If #7A is No, and #7B is missing, this domain is missing.

Measure	Description	Variable	Derivation / Comment	Imputation Approach if with Missing Components
		DLQI personal relationships domain	Sum of responses of questions #8 and #9: #8. How much has your skin created problems with your partner or any of your close friends or relatives? #9. How much has your skin caused any sexual difficulties?	If one question in a domain is missing, that domain is missing.
		DLQI treatment	Response of question #10: #10. How much of a problem has the treatment for your skin been, for example by making your home messy, or by taking up time?	If one question in a domain is missing, that domain is missing.
		DLQI total score	A DLQI total score is calculated by summing all 10 question responses, and has a range of 0 to 30 (less to more impairment) (Finlay and Khan 1994; Basra et al. 2008).	If two or more questions are missing, the total score is missing. Note: #7B could be a valid missing while #7A is not “No.” That is, #7 should be considered as one question.
		DLQI (0,1)	A DLQI (0,1) response is defined as a post-baseline DLQI total score of 0 or 1. A DLQI total score of 0 to 1 is considered as having no effect on a patient’s HRQoL (Khilji et al. 2002; Hongbo et al. 2005).	Missing if DLQI total score is missing
		DLQI (0)	A DLQI (0) response is defined as a post-baseline DLQI total score of 0.	Missing if DLQI total score is missing
		DLQI total score and domain scores change from baseline	Calculated as: observed DLQI (total score or domain scores) – baseline DLQI (total score or domain scores)	Missing if baseline or observed value is missing

For health outcomes measures, the following endpoints will be summarized descriptively at each scheduled visit for Period 2 and for Combined Periods 2 and 3, respectively (Analysis population: FAS Population for Period 2, Maintenance Dosing Period Population for Combined Periods 2 and 3):

- Change from baseline in Itch NRS score
- Number of patients who achieve Itch NRS  $\geq 4$  point reduction from baseline for patients who had baseline Itch NRS  $\geq 4$
- Change from baseline in DLQI total score and domains (i.e., symptoms and feelings, daily activities, leisure, work and school, personal relationships, and treatment)
- Number of patients who achieve DLQI (0, 1) and DLQI (0).

### 6.13. Safety Analyses

Safety will be assessed by AEs, laboratory analytes including neutrophil counts, vital signs, weight, and C-SSRS.

Overall AEs and treatment-emergent adverse events (TEAEs) will be summarized with frequencies. The duration of dosing exposure will also be summarized. Other safety measures will be reviewed by listings.

Summaries of overall AEs and TEAEs will be provided in patients with GPP and EP separately and total for Period 2 and for Combined Periods 2 and 3, respectively (Analysis population: FAS Population for Period 2, Maintenance Dosing Period Population for Combined Periods 2 and 3).

#### 6.13.1. Extent of Exposure

Exposure to study drug will be summarized descriptively for Period 2 and for Combined Periods 2 and 3, respectively (Analysis population: FAS Population for Period 2, Maintenance Dosing Period Population for Combined Periods 2 and 3).

A by-patient listing of exposure duration with number of active injections and total dose will be provided (Analysis population: FAS Population).

The duration of exposure will be calculated as:

$$\begin{aligned} \text{Duration of exposure (days)} \\ &= \text{Date of last visit (scheduled or unscheduled) in Treatment Period} \\ &\quad - \text{Date of first dose in Treatment Period} + 1 \end{aligned}$$

The number of patients in each of the following categories will be included in the summaries:

- $>0, \geq 7$  days,  $\geq 14$  days,  $\geq 30$  days,  $\geq 60$  days, and  $\geq 84$  days (Period 2). Note that patients may be included in more than 1 category.
- $>0$  to  $<7$  days,  $\geq 7$  to  $<14$  days,  $\geq 14$  to  $<30$  days,  $\geq 30$  to  $<60$  days,  $\geq 60$  to  $<84$  days,  $\geq 84$  days (Period 2)
- $>0, \geq 7$  days,  $\geq 14$  days,  $\geq 30$  days,  $\geq 60$  days,  $\geq 90$  days,  $\geq 120$  days, and  $\geq 140$  days (Combined Periods 2 and 3). Note that patients may be included in more than 1 category.

- >0 to <7 days, ≥7 to <14 days, ≥14 to <30 days, ≥30 to <60 days, ≥60 to <90 days, ≥90 to <120 days, ≥120 to <140 days, and ≥140 days (Combined Periods 2 and 3).

Total dose (in mg) is calculated by the number of active injections taken during the treatment period multiplied by a dose of 80 mg.

Total number of injections received will be derived using the response to the question “Was dose administered?” on the *Exposure as Collected* eCRF page and the actual dose description from IWRS study drug dispense dataset.

### 6.13.2. Adverse Events

Adverse events will be classified based upon the latest version of the MedDRA. Adverse events will be recorded at every study visit. Any condition starting on or after the date of informed consent will be considered an AE. Any preexisting condition which worsens in severity on or after the date of informed consent will be considered and recorded as an AE on the *Adverse Events (AE)* eCRF page from the date of worsening onwards.

A treatment-emergent adverse event (TEAE) is defined as an event that first occurred or worsened in severity after baseline and on or prior to the date of the last visit within the defined treatment period. Both the date/time of the event and the date/time of the dose (that is, injection) are considered when determining TEAEs. The TEAEs will be assigned to the study period to which it's considered treatment-emergent:

- The MedDRA lowest level term (LLT) will be used when classifying AEs as treatment-emergent.
- The maximum severity recorded for each LLT prior to the first dose date/time in the treatment period will be used as the pre-treatment severity for that LLT. If an event during the baseline period has missing severity, and the event persists during the treatment period, then it will be considered as treatment-emergent, regardless of the postbaseline level of severity. Adverse events with a missing severity during the treatment period will be considered treatment-emergent.
- Adverse events with a particular LLT will be classified as treatment-emergent if they first start on or after the first dose date/time in the treatment period (i.e., a patient has no preexisting conditions with that LLT), or if the severity is greater than the pre-treatment severity for that LLT. If a partial AE start date/time is present, the date/time will be compared as far as possible to the treatment start date/time in order to determine whether the event is treatment-emergent or not. If there is any doubt, the event will be flagged as treatment-emergent.

Overall AEs and TEAEs will be summarized for the following study periods and analysis populations:

- Period 2 (Analysis population: FAS Population)
- Combined Periods 2 and 3 (Analysis population: Maintenance Dosing Period Population).

The following summaries will be provided for Period 2 and for Combined Periods 2 and 3 (Analysis population: FAS Population for Period 2, Maintenance Dosing Period Population for Combined Periods 2 and 3):

- An overall summary of AEs including the number of patients who experienced TEAE, TEAE by maximum severity, death, SAE, TEAE possibly related to study treatment, discontinuation from the treatment due to an AE (including death), and treatment-emergent adverse events of special interest (AESIs)
- TEAE by maximum severity, system organ class (SOC) and preferred term (PT).

In general, events will be ordered by decreasing frequency in the total patient group (i.e., combined GPP and EP) within SOC and PT for sorting.

A by-patient listing of all AEs will be provided (Analysis population: FAS Population).

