Study I1F-JE-RHCV is a multicenter, open-label, post marketing clinical trial to evaluate the efficacy and safety of ixekizumab Q2W beyond Week 12 until Week 20 in patients with GPP and EP.

Treatment Arms and Duration:

Study I1F-JE-RHCV consists of 3 periods: a screening period of up to 30 days, a 12-week Induction Dosing Period, and an 8-week Maintenance Dosing period. All eligible patients will be administered 160 mg ixekizumab as 2 SC injections at Week 0 (baseline; Visit 2) followed by 80 mg as 1 injection at Week 2, 4, 6, 8 and 10. Patients who are inadequate responders (Global Improvement Score [GIS] ≥ 2 at Week 12 and based on the investigators' discretion) will be administered 80 mg as 1 injection at Week 12, 14, 16, and 18 or until they achieve a GIS score of 1.

Number of Patients:

A total of 12 patients will be enrolled so that at least 5 patients with EP and 5 patients with GPP who are inadequate responders (GIS ≥ 2 at Week 12 and based on the investigators' discretion) will continue to use ixekizumab beyond Week 12. Additional enrollment may occur and sample size may be increased, if no GPP or EP patients enter into Period 3 (Maintenance Dosing Period) of the study.

Statistical Analysis:

Primary analysis of efficacy, health outcome and safety measures will be conducted based on patients who continued ixekizumab 80 mg Q2W beyond Week 12 by disease type (ie, GPP and EP separately).

Baseline is defined as the last available value before the first dose in Period 2; in most cases, it will be the value recorded at Week 0 (Visit 2).

As this is a single arm study with very small sample size, no statistical inference will be performed.

Continuous data will be summarized in terms of the mean, standard deviation, minimum, maximum, median, and number of observations. Categorical data will be summarized as frequency counts.

2. Schedule of Activities

Table RHCV.1. Schedule of Activities

| Procedure | Screening Period (Period 1) | Treatment Period - Induction (Period 2) | | | | | Treatment Period - Maintenance (Period 3) | | | | ETV |
|---|-----------------------------|---|---------|---------|---------|---------|---|----------|----------|----------------|----------------|
| | V1 | V2 | V3 | V4 | V5 | V6 | V7 | V8 | V9 | V10 | |
| Study Week | - | 0 | 2 | 4 | 8 | 12 | 14 | 16 | 18 | 20 | |
| Visit Intervals | -30d to -7d | 0 | 14 ± 2d | 28 ± 4d | 56 ± 4d | 84 ± 2d | 98 ± 2d | 112 ± 2d | 126 ± 2d | 140 ± 2d | NA |

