10.3.4.1. Adverse Events

Adverse events are classified based upon the Medical Dictionary for Regulatory Activities (MedDRA). A TEAE is defined as an event that first occurred or worsened in severity after baseline and on or prior to the date of the last visit within the treatment period. Both the date/time of the event onset and the date/time of the first study drug injection are considered when determining TEAEs. Treatment-emergent adverse events will be assigned to the treatment period in which they first occurred or worsened.

An overall summary of AEs will be provided for each of the treatment periods, including the number of patients who experienced TEAEs, TEAEs by maximum severity, deaths, SAEs, TEAEs related to study drug, discontinuations from the treatment due to an AE, and treatment-emergent AESIs. By-patient listings of TEAEs, SAEs including deaths, AEs that lead to treatment discontinuation, and AESIs will be provided.

Adverse events of special interest will be identified by a standardized MedDRA query (SMQ) or a Lilly defined MedDRA preferred term listing.

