## **6.9. Treatment Compliance**

Throughout treatment periods, enrolled patients will record information in a Study Drug Administration Log (captured in the *Exposure as Collected* eCRF page), including the date, time, and anatomical location of administration of investigational product, package number, who administered the investigational product, and the reason if the investigational product was not fully administered.

Treatment compliance for each patient will be calculated as:

$$\text{Treatment compliance (\%)} = 100 \times \frac{\text{Total number of injections administered}}{\text{Total number of injections prescribed}}$$

- For patients who complete Period 2, the number of injections prescribed (that is, expected) during Period 2 will be equal to 7 (2 injections at Week 0 and 1 injection every 2 weeks from Week 2 to Week 10).
- For patients who discontinue during Period 2, the number of injections prescribed during Period 2 can be derived from the IWRS study drug dispense dataset.
- For patients who complete Period 3, the number of injections prescribed (that is, expected) during Period 3 will be equal to 4 (1 injection every 2 weeks from Week 12 to Week 18).
- For patients who discontinue during Period 3 or who complete study treatment because of GIS = 1 (i.e., Responder) before Week 18, the number of injections prescribed during Period 3 can be derived from the IWRS study drug dispense dataset.
- The total number of injections administered will be derived using the response to the question “Was dose administered?” on the *Exposure as Collected* eCRF page.

A patient will be considered overall compliant with study treatment if he/she misses no more than 20% of the expected doses, does not miss 2 consecutive doses (all injections at an injection week are counted as 1 dose), and does not over-dose (that is, take more injections at the same time point than specified in the protocol).

The treatment compliance (continuous variable) and the number of patients that are compliant and non-compliant (categorical variable) will be summarized for patients with GPP and EP separately and total for Period 2 and for Combined Periods 2 and 3, respectively (Analysis population: FAS Population for Period 2, Maintenance Dosing Period Population for Combined Periods 2 and 3).

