### 6.10.2. Concomitant Therapy

Concomitant therapy for Period 2 is defined as the therapy that starts before, on, or after the first day of study treatment of Period 2 and before the last visit date of Period 2, and continues into Period 2, that is, either no end date (the therapy is ongoing) or an end date on or after the first day of study treatment of Period 2. Concomitant therapy will belong to Period 2 if the therapy starts and ends on the exact same day as the first day of study treatment of Period 2.

Concomitant therapy for Period 3 is defined as the therapy that starts before, on, or after the last visit date of Period 2 and continues into Period 3, that is, either no end date (the therapy is ongoing) or an end date after the last visit date of Period 2. Concomitant therapy will belong to Period 3 if the therapy starts and ends on the exact same day as the last visit date of Period 2.

If a partial medication start date is present, the following imputation rules will be utilized in the analysis:

- If either month or month and day are missing, then use January 1.
- If only day is missing, impute the first day of the month.
- If there is any doubt, the medication will be flagged as concomitant.

The number of patients with the following will be presented for patients with GPP and EP separately and total for Period 2 and for Period 3, respectively (Analysis population: FAS Population for Period 2, Maintenance Dosing Period Population for Period 3):

- Concomitant therapy (captured in the *Concomitant Therapy* eCRF page) by WHO ATC Level 4 and WHO drug generic name.

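### The Period 2 adverse event window closes on the Week 12 visit date, so a same-day reaction to the first Period 3 injection also enters the Period 2 table

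*SAP*

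**What the plan says.** **When the window opens and closes.** Under SAP 6.13.2 an event is treatment-emergent "if they first start on or after the first dose date/time in the treatment period", or if it is more severe than before treatment. The window ends with events "and on or prior to the date of the last visit within the defined treatment period". The opening bound carries a clock time; the closing bound is a calendar date.

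**Which period owns the Week 12 injection.** SAP 5.1 makes Week 12 (Visit 6) the last visit of Period 2. The Schedule of Activities (Protocol Section 2) marks drug administration at Visit 6. The Protocol synopsis says continuing patients "will be administered 80 mg as 1 injection at Week 12, 14, 16, and 18". SAP 6.9 expects 7 injections in Period 2, the last at Week 10, and says the number "during Period 3 will be equal to 4 (1 injection every 2 weeks from Week 12 to Week 18". The Week 12 injection therefore belongs to Period 3.

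**Other rules for the same day.** For concomitant therapy, SAP 6.10.2 has a tie-break: a therapy "will belong to Period 3 if the therapy starts and ends on the exact same day as the last visit date of Period 2". Adverse events have no such tie-break. Protocol 10.3.4.1 gives only the principle: "Treatment-emergent adverse events will be assigned to the treatment period in which they first occurred or worsened".

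**What is tabulated.** SAP 6.13.2 summarizes adverse events for Period 2 (FAS Population) and for Combined Periods 2 and 3 (Maintenance Dosing Period Population). It plans no table for Period 3 alone.

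**The concern.** For a continuing patient, two periods share the Week 12 visit date, and the injection that opens the second is given on that date. Because the closing bound ignores clock time, the Period 2 window stays open for the rest of the day, after continued dosing has begun. Injection-site and hypersensitivity reactions are the events most likely to start within hours of a dose, and both are adverse events of special interest.

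At stake is the accuracy of the Period 2 table. It is meant to describe induction, yet it could contain a reaction to the first continued dose, and continued dosing is what the trial was set up to study. The text also leaves room for two programmers to produce different Period 2 tables.

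**Working it through.** **1. The plan's injection counts.** Period 2: 2 (Week 0) + 5 (Weeks 2, 4, 6, 8, 10) = 7, matching SAP 6.9, on 6 dosing days. Period 3: Weeks 12, 14, 16, 18 = 4, also matching. Week 12 is the first Period 3 injection.

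**2. The rule applied literally.** Assume Visit 6 is on day 84 and the injection is given at 10:00 during the visit. An event is in Period 2 if it starts at or after the first-dose date/time and its start date is no later than the Visit 6 date.

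| Start of a new event | Period 2, as written | Period 2, if closed at the Week 12 dose time |
|---|---|---|
| 1 hour before the injection | yes | yes |
| 2 hours after | yes | no |
| 13 hours after, same date | yes | no |
| Next day | no | no |

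Only the remaining hours of one day are in question.

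**3. Does any other text close Period 2 at the dose?** SAP 6.13.2 says: "Both the date/time of the event and the date/time of the dose (that is, injection) are considered when determining TEAEs". The bullets that follow use the dose time only for the first dose in the period, to fix pre-treatment severity and the start of the window. The protocol's counterpart is narrower still: "Both the date/time of the event onset and the date/time of the first study drug injection are considered when determining TEAEs". Neither sets a closing time. The SAP's rule for partial times flags doubtful events as treatment-emergent, but it does not choose between periods.

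**4. Who can be affected.** A patient must continue past Week 12, be dosed on the visit date, and have an event that is new or worse than before treatment. In the earlier study cited in SAP 5.2, 1 of 5 GPP and 1 of 8 EP patients had GIS = 1 at Week 12, so 11 of 13 did not. Then 12 × 11/13 = 10.2, in line with the planned 5 + 5 = 10.

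**5. Chance that the Period 2 count changes.** The documents give no same-day reaction rate, so let p be the chance per injection, assumed constant and independent. The table counts patients, so someone who already had the reaction on one of the 6 earlier dosing days adds nobody. The chance that a given patient is newly added is p(1 − p)^6, and for n continuing patients the chance of at least one is 1 − [1 − p(1 − p)^6]^n.

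| p (assumed) | p(1 − p)^6 | At least one, n = 10 | At least one, n = 5 |
|---|---|---|---|
| 2% | 0.0177 | 16% | 9% |
| 5% | 0.0368 | 31% | 17% |
| 10% | 0.0531 | 42% | 24% |

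The n = 5 column is included because SAP 5.2 also speaks of approximately 5 patients at maximum continuing, without saying whether that is per disease or in total. The expected number added with n = 10 is 10 × p(1 − p)^6 = 0.18, 0.37 or 0.53 patients. A repeat reaction of greater severity would add no patient but could move one between rows of the maximum-severity table.

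**The case against.** The strongest reply is that almost nothing depends on this. Anyone who receives a Period 3 dose is in the Maintenance Dosing Period Population, so the event is counted in the Combined table in any case, and the by-patient listings show it. With about 12 patients and no inference, those listings are a main tool of the safety review. This stands, and it limits the point to the Period 2 table.

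A reader might infer that these events are credited to induction instead of to continued treatment, or that comparing the two tables would misstate Period 3 risk. The documents support neither. The Combined table contains Period 2 and covers only continuing patients, whereas the Period 2 table covers everyone treated. Period 3 cannot be obtained by subtracting one from the other, with or without a change.

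A reader might also take SAP 6.10.2 as proof that the SAP contradicts itself. It is weaker than that: concomitant therapy is tabulated for Period 2 and Period 3 separately, so it needs a tie-break, while the adverse event tables are cumulative. The exposure formula in SAP 6.13.1 in fact agrees with the current window, because 84 − 0 + 1 = 85 days includes the whole Week 12 day.

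Finally, the sentence on event and dose times could be read as leaving room for a cut at the injection. It does leave room, but it states no rule. The split of injections in SAP 6.9 and the assignment principle in Protocol 10.3.4.1 still have no boundary rule to put them into effect on this day.

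**Conclusion.** The point holds as a minor boundary error. As written, SAP 6.13.2 puts a new or worsened reaction that starts after the Week 12 injection on the same date into the Period 2 (FAS) adverse event and special-interest table, although SAP 6.9 assigns that injection to Period 3. The Combined table and the listings are unaffected.

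The likely effect is no patient or one. The chance of at least one is about 16%, 31% or 42% for assumed rates of 2%, 5% or 10% per injection. These figures rest on about 10 continuing patients, all dosed on the visit date, and on a constant, independent rate. They fall if fewer patients continue, which also depends on the investigator's discretion, or if the Week 12 dose is given later; Protocol 7.2.1 allows up to 4 days. No conclusion about efficacy or about overall safety in the continuing patients turns on it.

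**What to change.** Add to SAP 6.13.2:

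> For patients who receive a Period 3 dose, the Period 2 TEAE window ends immediately before the date/time of the first Period 3 injection (otherwise on the date of the last Period 2 visit). Events starting or worsening at or after that time are counted only in Combined Periods 2 and 3. If the event time is missing on that date, injection-site and hypersensitivity events are treated as occurring after the injection.

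The cost is this wording and a small programming change; the treatment-emergent rule already relies on event and injection date/times, so no new data are needed.

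There are three side effects to accept:

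- The Period 2 event window would differ slightly, on the Week 12 day, from the Period 2 exposure window in SAP 6.13.1.
- Unrelated events starting later that day would also leave the Period 2 table, while staying in the Combined one.
- If the Week 12 dose is delayed past the visit, Period 2 would stay open until that dose is given, so events in the gap would count in Period 2.
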